### **4.4 Measurement**

#### **4.4.1 Schedule of Measurement**

**Risk Factor Questionnaire:** A new questionnaire for the South Africa setting has been developed in English from a template previously used in Brazil for the REDS-II study. It assesses risk exposure over two intervals; ever and within the 6 months preceding the index donation. **Appendix 7** provides content for the risk factor questionnaire. The interview will be an audio computer-assisted structured interview (ACASI) as done successfully in a previous REDS-II and current REDS-III study in Brazil. Participants will be able to read and hear the questions using

ear phones for privacy. Interviews will be conducted using portable laptops so as to provide ease of access to the study participants. The ACASI interview will be conducted in a private location, ideally at a SANBS blood centre, but we will allow the interview to be conducted at the study participants' location of preference, such as at home. We propose to use 10 laptop computers (2 per zone) which will permit simultaneous interviews at different locations throughout SANBS. It will take approximately 30-45 minutes to complete the questionnaire. Interview data will be backed-up from the laptops onto a server or dedicated desktop computer at SANBS central offices on a daily basis, and uploaded weekly via a secure FTP site to the Data Coordinating Centre.

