**SECTION H - ALCOHOL AND DRUG USE**

**READ and HEARD:** Now we are going to ask you some general questions regarding alcohol and drug use. Some types of alcohol or drug use can be related to the risk of becoming infected with HIV or HBV. Once again, the following questions are intended to help us determine how to improve the safety of donated blood. We are asking you to respond as truthfully as you can. The answers are confidential. Your individual responses will not be known by SANBS. Your answers will be reported together with all other people who complete the questionnaire.

H1. How often do you drink beer, wine, liquor, or mixed drinks? (Choose one)

- |    |                             |                   |
|----|-----------------------------|-------------------|
| 0  | Never                       | Skip to H4 |
| 1  | 1-3 times per month or less |                   |
| 2  | 1-2 times per week          |                   |
| 3  | 3-6 times per week          |                   |
| 4  | Everyday                    |                   |
| 97 | Don't Know                  |                   |
| 98 | Refuse to Answer            |                   |

H2. On average how many drinks do you have each time you drink? (When answering, one drink is a glass of wine or a beer or a mixed drink.)

Number of drinks         

997 Don't Know

H3a. Have you ever used dagga, marijuana, or hashish? (Choose one)

- |    |                  |                    |
|----|------------------|--------------------|
| 0  | No               | Skip to H4a |
| 1  | Yes              |                    |
| 97 | Don't Know       |                    |
| 98 | Refuse to Answer |                    |

H3b. When was the first year you used dagga, marijuana or hashish?

— — — — YYYY

2097 Don't Know (Year)

2098 Refuse to Answer (Year)

***If H3b is less than B2 then READ and HEARD: "The year that you entered for first year of dagga, marijuana, or hashish drug use is smaller than the year you were born. Please correct the year of your first dagga, marijuana, or hashish drug use." (Returns to H3b)***

H3c. When was the last year you used dagga, marijuana or hashish?

— — — — YYYY

2097 Don't Know (Year)

2098 Refuse to Answer (Year)

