***If H3c is less than H3b then READ and HEARD: "The year that you entered for last year of dagga, marijuana, or hashish drug use is smaller than the year of your first reported dagga, marijuana, or hashish drug use. Please correct the last year of your dagga, marijuana, or hashish drug use." (Returns to H3c)***

H4a. Have you ever used whoonga which is also known as nyaope? (Choose one)

0 No **Skip to H5a**

1 Yes

97 Don't Know

98 Refuse to Answer

H4b. When was the first year you used whoonga or nyaope?

— — — — YYYY

2097 Don't Know (Year)

2098 Refuse to Answer (Year)

**If H4b is less than B2 then READ and HEARD: "The year that you entered for first year of whoonga or nyaope drug use is smaller than the year you were born. Please correct the year of your first whoonga or nyaope drug use." (Returns to H4b)**

H4c. When was the last year you used whoonga or nyaope?

— — — —      YYYY

2097      Don't Know (Year)

2098      Refuse to Answer (Year)

**If H4c is less than H4b then READ and HEARD: "The year that you entered for last year whoonga or nyaope drug use is smaller than the year of your first reported whoonga or nyaope drug use. Please correct the last year of your whoonga or nyaope drug use." (Returns to H4c)**

H5a. Have you ever used any non-injected drugs (drugs that are smoked, snorted or taken orally), examples include tik, mandrax, "glue", cocaine (crack), methamphetamines (crystal), ecstasy ("E") and LSD? (Choose one)

0      No      **Skip to H7**

1      Yes

97      Don't Know

98      Refuse to Answer

H5b. When was the first year you used non-injected drugs?

— — — —      YYYY

2097      Don't Know (Year)

2098      Refuse to Answer (Year)

**If H5b is less than B2 then READ and HEARD: "The year that you entered for first year of non-injected drug use is smaller than the year you were born. Please correct the year of your first non-injected drug use." (Returns to H5b)**

H5c. When was the last year you used non-injected drugs?

— — — —      YYYY

2097      Don't Know (Year)

2098      Refuse to Answer (Year)

***If H5c is less than H5b then READ and HEARD: "The year that you entered for last year non-injected drug use is smaller than the year of your first reported non-injected drug use. Please correct the last year of your non-injected drug use." (Returns to H5c)***

H6. If you have smoked or snorted drugs, did you share pipes or straws with another person? (Choose one)

1      Always

2      Sometimes

3      Never

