97      Don't Know

98      Refuse to Answer

H7a. Have you ever used injection drugs (examples include heroin, cocaine, and amphetamines)? (Choose one)

0      No

1      Yes

97      Don't Know

98      Refuse to Answer

H7b. When was the first year you used injected drugs?

- — — —      YYYY
- 2097      Don't Know (Year)
- 2098      Refuse to Answer (Year)

**If H7b is less than B2 then READ and HEARD: "The year that you entered for first year of injected drug use is smaller than the year you were born. Please correct the year of your first injected drug use." (Returns to H7b)**

H7c. When was the last year you used injected drugs?

- — — —      YYYY
- 2097      Don't Know (Year)
- 2098      Refuse to Answer (Year)

**If H7c is less than H7b then READ and HEARD: "The year that you entered for last year of injected drug use is smaller than the year of your first reported injected drug use. Please correct the last year of your injected drug use." (Returns to H7c)**

H8a. Have you ever injected yourself with any substances including vitamins, steroids, or hormones which were not prescribed by a doctor or nurse? (Choose one)

- 0      No                      **Skip to Section I**
- 1      Yes
- 97      Don't Know
- 98      Refuse to Answer

H8b. Have you ever shared needles or syringes with another person to inject yourself with any substance including drugs, vitamins, steroids or hormones which were not prescribed by a doctor? (Choose one)

0 No

1 Yes

97 Don't Know

98 Refuse to Answer

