**SECTION I - MEDICAL HISTORY**

**READ and HEARD:** *In the next set of questions we will ask about some medical treatments you may have had.*

I1. Have you ever had a blood transfusion? (Choose one)

- 0 No **Skip to I5**
- 1 Yes
- 97 Don't Know
- 98 Refuse to Answer

I2. How many transfusion episodes have you had?

— —

- 97 Don't Know
- 98 Refuse to Answer

I3. When was the first year you received a transfusion?

— — — —

- 9997 Don't Know
- 9998 Refuse to Answer

**If I3 is less than B2 then READ and HEARD:** *"The year that you entered for first year transfusion is smaller than the year you were born. Please correct the year of your first transfusion." (Returns to I3)*

14. When was the last year you received a transfusion?

— — — —

9997 Don't Know

9998 Refuse to Answer

***If 14 is less than 13 then READ and HEARD: "The year that you entered for last year of transfusion is smaller than the year of your first reported transfusion. Please correct the last year of your transfusion." (Returns to 14)***

15. Have you ever had minor or major surgery in a hospital, doctor's room, or dentist's office? (Choose one)

0 No ***Skip to 19***

1 Yes

97 Don't Know

98 Refuse to Answer

16. In the 6 months before your donation, have you had minor or major medical surgery in hospital? (Choose one)

0 No

1 Yes

97 Don't Know

98 Refuse to Answer

17. In the 6 months before your donation, have you had any surgical procedures in your doctor's room or office? (Choose one)

- 0 No
- 1 Yes
- 97 Don't Know
- 98 Refuse to Answer

18. In the 6 months before your donation, have you had any tooth extractions or another dental procedure at a dentist's office? (Choose one)

- 0 No
- 1 Yes
- 97 Don't Know
- 98 Refuse to Answer

19. Have you ever had an endoscopy (a medical test where a flexible tube is used to look inside of your throat and digestive system) or colonoscopy (a medical test where tube is used to look inside your colon/large intestine)? (Choose one)

- 0 No **Skip to I11**
- 1 Yes
- 97 Don't Know
- 98 Refuse to Answer

I10. In the 6 months before your donation, have you had an endoscopy or colonoscopy? (Choose one)

- 0 No
- 1 Yes
- 7 Don't Know
- 8 Refuse to Answer

I11. Have you ever been immunized / vaccinated against Hepatitis B?

- 0 No
- 1 Yes
- 97 Don't Know
- 98 Refuse to Answer

I11b. If yes, can you tell us your age when you were immunized/vaccinated against Hepatitis B?

\_\_\_\_\_ years old

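### The donor's own drug use and transfusion are dated only to a calendar year, and needle sharing not at all, so the six-month exposure that the protocol says it measures is not reliably recoverable for recent users

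*Protocol*

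**What the plan says.** Section 4.4.1 (Schedule of Measurement) describes the risk factor questionnaire in one sentence: "It assesses risk exposure over two intervals; ever and within the 6 months preceding the index donation".

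In Appendix 7, Section H, each block on the donor's own drug use asks whether it ever happened, then the first and last calendar year. The recency items are "When was the last year you used dagga, marijuana or hashish" (H3c), "When was the last year you used whoonga or nyaope" (H4c), "When was the last year you used non-injected drugs" (H5c) and "When was the last year you used injected drugs" (H7c). Sharing of pipes or straws (H6) has no time frame. Self-injection (H8a) reads "Have you ever injected yourself with any substances including vitamins, steroids, or hormones which were not prescribed by a doctor or nurse", and needle sharing (H8b) begins "Have you ever shared needles or syringes with another person"; neither has a dated follow-up. In Section I, transfusion (I1 to I4) asks ever, number of episodes, first year and last year: "When was the last year you received a transfusion".

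Section 3 gives injection drug use as an example of the high-risk behaviour that donor selection looks for. Section 4 (Objectives) and section 4.9 do not name drug use, needle sharing or transfusion among the hypothesised predictors. Section 4.9 says that other possible predictors will also be examined.

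**The concern.** Objective 1 concerns incident infection, so the relevant exposure is recent exposure, and section 4.4.1 promises it. A calendar year does not map onto a six-month window that ends on an arbitrary donation date, and an undated lifetime item does not map onto it at all. This is a matter of data collection: no later analysis plan can recover a window that was never asked about.

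The gap looks unintended, because nearby items do use the six-month window. Item G1b asks whether a sexual partner in that window injected drugs, yet the donor's own injecting is not asked about on that scale.

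What is at stake is the odds ratio for recent drug use, injecting and transfusion. The analyst must either use lifetime exposure or build a proxy from calendar years, and both mix recent with past exposure.

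**Working it through.** **Step 1: time frame of each item (Appendix 7).**

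| Exposure | Items | Recorded |
|---|---|---|
| Cannabis; whoonga; other non-injected drugs; injected drugs | H3, H4, H5, H7 | ever, first year, last year |
| Sharing pipes or straws | H6 | no time frame |
| Self-injection; needle sharing | H8a; H8b | ever only |
| Transfusion | I1–I4 | ever, episodes, first year, last year |
| *Contrast:* partner who injects | G1b | 6 months |
| *Contrast:* surgery, dental, endoscopy | I6–I8, I10 | 6 months |
| *Contrast:* injection by a traditional healer | I12 | 6 months |
| *Contrast:* jail, tattoo, piercing | J1, J6, J9 | 6 months |
| *Contrast:* needle-stick, splash at work | K2, K3 | 6 months |

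No other item supplies a six-month version of the first four rows. H7c does not bound H8a or H8b, because those two also cover vitamins, steroids and hormones.

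**Step 2: what a last-use year reveals.** I took all 365 donation dates of a year and asked whether the possible last-use dates lie wholly, partly or not at all within the six months before donation. Interview lag is an assumption: 0 days for controls, who are invited after donating (section 4.2.2, Control Recruitment and Enrollment), and 30 days for cases, who answer at a return visit or later (section 4.2.2, Participant Enrollment). The only stated figure, about one month, is for Objective 3 enrolment.

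- Last year two or more calendar years before the donation year: certain no on every date.
- Last year = previous year, July–December donation: certain no.
- Last year = previous year, January–June donation: ambiguous on 100% of dates; 0.5% to 50% of possible days fall in the window (mean 25%).
- Last year = donation year, July–December donation, same-day interview: ambiguous on 99.5% of dates; 50% to 100% in the window (mean 70%).
- Last year = donation year, January–June donation, same-day interview: certain yes.
- Last year = donation year, interview 30 days later: ambiguous on 100% of dates in both halves, because last use may follow the donation. The share in the window runs from 1/31 = 3% (donation 1 January) to 182/212 = 86% (donation 1 July).

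**Step 3: illustrative effect on the odds ratio.** None of these inputs is in the protocol: true OR 3 for recent use and 1 for past use; recent use in 2–5% and past use in 6–12% of controls; last use uniform over the 3 years before donation; donations uniform over the year; equal error in cases and controls. Let u be the donation time within the year, s the share of recent users flagged and f the share of past users flagged.

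- Same-year rule: s = E[min(u, 0.5)]/0.5 = 0.375/0.5 = 0.75; f = E[max(u − 0.5, 0)]/2.5 = 0.125/2.5 = 0.05.
- Same-or-previous-year rule: s = 1; f = E[u + 0.5]/2.5 = 1.0/2.5 = 0.40.

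With control prevalences r (recent) and p (past):

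OR = [(3sr + fp) / (1 + 2r − 3sr − fp)] ÷ [(sr + fp) / (1 − sr − fp)]

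- Same-year, r = 0.02, p = 0.12: (0.051/0.989) ÷ (0.021/0.979) = 2.40.
- Same-year, r = 0.05, p = 0.06: (0.1155/0.9845) ÷ (0.0405/0.9595) = 2.78.
- Same-or-previous, r = 0.02, p = 0.12: (0.108/0.932) ÷ (0.068/0.932) = 1.59.
- Same-or-previous, r = 0.05, p = 0.06: (0.174/0.926) ÷ (0.074/0.926) = 2.35.
- Lifetime item (s = f = 1), same two settings: 0.18/0.14 = 1.29 and 0.21/0.11 = 1.91.

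Under the same-or-previous-year rule, the share of flagged controls who are truly recent is 0.02/0.068 = 29% to 0.05/0.074 = 68%.

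**The case against.** Four points can fairly be made on the other side.

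First, a reader might infer that the six-month variable cannot be derived for anyone. Step 2 does not support that. Never-users and long-past users are a certain no. Section 4.10.1 provides for linking the donation record to the questionnaire, so the donation date resolves some others. This stands. What remains unresolved is most recent users and everyone with a yes on H8a or H8b.

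Second, a three-year uniform last-use pattern is harsh for a habitual behaviour. If time since last use were exponential with mean 3 months (also an assumption), the same-year rule would flag 83% of recent users with 95% of flags correct, and the wider rule would have 87% of flags correct. For active users the loss could thus be small. That argument does not carry over to a one-off event such as transfusion, and it does nothing for the undated items.

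Third, a reader might infer that the bias must run toward 1. That requires equal error in cases and controls, which the design does not secure: cases answer later, and the year items are not limited to the time before donation. The direction is therefore uncertain.

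Fourth, these exposures are outside the named hypotheses and outside the power basis in section 4.8, and the protocol gives no prevalence for them in accepted donors. This stands, and it limits the weight of the point.

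**Conclusion.** The instrument does not match section 4.4.1 for the donor's own drug use, self-injection, sharing of equipment or transfusion. Six-month exposure is not reliably derivable for recent users or recent transfusion recipients, and not derivable at all for those who ever self-injected or shared needles. The gap concerns injection drug use and self-injection; injection by a traditional healer (I12) does have a six-month item.

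The size is illustrative only. On the assumptions in step 3, a true odds ratio of 3 is observed as about 2.4 to 2.8 with a same-year rule and 1.6 to 2.4 with a same-or-previous-year rule. With differential error, neither range nor direction is assured.

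A reader might take this as undermining the primary hypotheses of Objectives 1a and 1b. It does not: none of them uses these items. The harm is to the wider behavioural risk-factor analysis. The change is worth making because it is cheap before data collection and the loss cannot be repaired afterwards.

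**What to change.** After a yes to H3a, H4a, H5a, H7a, H8a, H8b and I1, add one yes/no item with the six-months-before-donation stem already used in Sections E, G, I and J. Put H6 on the same window. State in section 4.9 that these items, not the calendar-year items, define recent exposure in Objective 1. Because the stem ends at the donation, it also excludes use after donation in the same way for cases and controls.

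Cost: seven short conditional items and one re-windowed item, seen only by respondents with a relevant yes, plus an edit to the ACASI program. Section 4.6 requires OMB approval of the instruments and allows up to nine months for it. The protocol does not say whether clearance has been obtained; if it has, the edit would need to go through as a change to the instrument.

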**YEAR2 = A5 - 1**

A6. Research Staff Initials: \_\_\_ \_\_\_ \_\_\_ \_\_\_

A7. Type of Participant (Choose one)

- 1 Study group 1 (won't appear on screen: HIV case)
- 2 Study group 2 (won't appear on screen: HBV case)
- 3 Study group 3 (won't appear on screen: Control)

**INSTRUCTION to RESEARCH STAFF: If study participant is not already sitting at the computer, at this time please make sure the study participant is sitting at the computer and has put the headphones on.**

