***If F9 is equal to South Africa skip to F9b which province, Else skip to F10.***

***If F9 is equal to Other skip to F9c, Else skip to F10.***

F9b. Which province in South Africa is partner 1 from?

- 1 Eastern Cape
- 2 Free State
- 3 Gauteng
- 4 KwaZulu Natal
- 5 Limpopo
- 6 Mpumalanga
- 7 North West
- 8 Northern Cape
- 9 Western Cape
- 97 Don't Know
- 98 Refuse to answer

F9c. Please specify which country partner 1 is from:

-----

F10a. Do you live with partner 1?

- 1 Yes

2 No

99 Refuse to answer

F10b. Is partner 1 currently working (Choose one)?

1 Yes, self-employed

2 Yes, employed full or part-time

3 No, unemployed **SKIP to F11**

97 Don't know

98 Refuse to Answer

F10c. What type of work is partner 1 doing?

- 0 Mining
- 1 Transport/cargo delivery
- 2 Military/police
- 3 Medical/healthcare
- 4 Business/sales/retail
- 5 Farming
- 6 Teacher/ education/ student
- 7 General labour (domestic worker, gardener, janitorial)
- 8 Civil service (examples including working in government office, post office)
- 9 Other
- 97 Don't Know
- 98 Refuse to Answer

F10d. *If F10c=10 Else SKIP* If Other, What is partner 1's occupation?

---

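### Several printed skip and code lines in the risk questionnaire (Protocol, Appendix 7) lose, or can lose, risk-factor data; minor, and cheap to correct before programming

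*Protocol*

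**What the plan says.** All items are in Protocol, Appendix 7, which Section 4.4.1 gives as the content of the self-completed computer interview.

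- **Dental care (Section I).** I5 asks about ever having had minor or major surgery in a hospital, doctor's room or dentist's office. No goes to I9, past I8, which asks about the six months before donation: "have you had any tooth extractions or another dental procedure at a dentist's office".
- **Partner's occupation (Section F).** F10c numbers its list from 0 (Mining) to 9 (Other). The free-text follow-up F10d carries the condition "If F10c=10 Else SKIP".
- **Partner's country (Section F).** The first rule after F9 reads "If F9 is equal to South Africa skip to F9b which province, Else skip to F10". A second rule sends Other to F9c and ends with the same instruction for everyone else.
- **Participant type (Section A).** A7, "Type of Participant (Choose one", offers HIV case, HBV case or control. Section L is routed on it: L1 to L8 for HIV cases, L9 for HBV cases.
- **Needle sharing (Section H).** H7a asks "Have you ever used injection drugs (examples include heroin, cocaine, and amphetamines". H8a then asks "Have you ever injected yourself with any substances including vitamins, steroids, or hormones which were not prescribed by a doctor or nurse? (Choose one", and No leaves the section. That bypasses H8b, which asks "Have you ever shared needles or syringes with another person to inject yourself with any substance including drugs".
- **Pipe sharing (Section H).** Dagga (H3a) and whoonga (H4a) have their own items. H5a asks about non-injected drugs, and No goes to H7, past H6: "If you have smoked or snorted drugs, did you share pipes or straws with another person".

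**The concern.** A skip rule should never be narrower than the item it guards, and a follow-up should open on a code that exists. Where either fails, the answer is structurally missing for some of the people the item was written for. The interview is completed alone after the first demographic items, so no interviewer is there to notice a wrong skip. The missing-data methods in Section 4.9 cannot restore a field that no respondent is ever shown.

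The exposures at stake are dental procedures, needle and pipe sharing, and partner origin and occupation, together with the opinion and treatment questions for donors with both infections. Section 3 lists injection drug use among the exposures on which donor selection concentrates, and H8b is the only needle-sharing item in Section H. Sections 1 and 3 both foresee donors recently infected with both viruses.

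**Working it through.** The Protocol gives no figure to reproduce here. The check traces each printed rule for every possible answer.

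**Fail as printed, if the respondent answers as worded**

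1. *I5 to I8.* I5 = No: I8 not asked. I5 = Yes, Don't Know or Refuse: I8 asked. A donor whose only dental contact was a non-surgical procedure correctly answers No and is never asked.
2. *F10c to F10d.* Codes in F10c are 0 to 9, 97 and 98. The trigger, 10, is not among them, so F10d never opens. The donor's own occupation item, B13b, runs from 1 to 10 with Other = 10, and its follow-up opens on 10. The partner version therefore looks like a renumbering slip. The block repeats for up to five partners.
3. *F9 rules.* With the first rule applied first, 1 (South Africa) goes to F9b and everything else, including 10 (Other), goes to F10, so F9c is missed for Other. With the second rule applied first, 10 goes to F9c and everything else, including 1, goes to F10, so F9b is missed for South Africa. Neither order works. F9b also has no exit rule, so a respondent with a South African partner falls into F9c and is asked to specify the country.
4. *A7 to Section L.* Codes are 1, 2 and 3. A donor with both infections entered as 1 gets L1 to L8, and one entered as 2 gets L9 only. For size, Section 3 says about 2.4% of donors with confirmed HIV or HBV were co-infected, and Section 4.1 plans 300 + 150 = 450 cases: 0.024 × 450 = 10.8, about 11. This is an illustration only, because the 2.4% is not a rate of recent dual infection.

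**Fail only for some readings of the gate**

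5. *H7a and H8a to H8b.* H8a = No: H8b not asked, whatever H7a says. H8a = Yes, Don't Know or Refuse: H8b asked. H7a plays no part.
6. *H3a, H4a and H5a to H6.* H5a = No: H6 not asked, whatever H3a and H4a say. H5a = Yes, Don't Know or Refuse: H6 asked. In addition, H1 = Never skips to H4, so non-drinkers are not asked about dagga at all.

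The number lost in 5 and 6 is respondents × share who used the drug × share of users who answer No at the gate. Planned respondents are 300 + 150 + 900 = 1,350. The Protocol gives neither share. On assumed shares of use, with the share answering No running from 0 to 1:

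| Item | Assumed share of use | Users among 1,350 | Lost |
|---|---|---|---|
| H8b | 1% | 13.5 | 0 to about 13 |
| H6 | 10% | 135 | 0 to 135 |
| H6 | 20% | 270 | 0 to 270 |

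These ranges show only that the loss cannot be pinned down.

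**The case against.** A reader might infer that the routing withholds needle sharing from drug injectors and pipe sharing from dagga and whoonga smokers. The text does not support that. H8a asks about any substances, and its examples do not limit it. H5a is defined by route of use, which includes smoking. A respondent who reads either gate literally answers Yes and reaches the item. What stands is narrower. The drugs concerned have just had their own questions and are absent from the gate's examples, and H8b names drugs where H8a does not, so a No from a user is plausible.

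A reader might also infer that a donor with both infections can appear in only one case group. Section 4.2.1 allocates NAT-yield cases on confirmatory laboratory results, and Section 4.10.1 links laboratory and questionnaire data by donation and participant number. Such a donor can therefore be identified and counted under both 1a and 1b. What is lost is L9 or L1 to L8.

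Other points in the plan's favour also hold. Code 9 for partner's occupation and code 10 for partner's country are still stored, so only the free text is lost. The intent of the F9 rules is easy to guess. I5 mentions a dentist's office, so a donor who regards an extraction as minor surgery passes the gate. Appendix 7 still carries open drafting queries (at the circumcision item and at L5), and Section 4.11 puts pilot testing before enrolment, where some slips would surface. None of this makes the printed lines right, and a pilot would not readily show an item that silently fails to appear.

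**Conclusion.** Four defects are established by the printed lines alone: the surgery gate before the dental item, the impossible trigger for F10d, the conflicting F9 rules with the fall-through from F9b, and the missing participant code for dual infection. The loss of F10d is complete: 100% of partners coded Other have no free text. The dual-infection loss is likely to be small, about 11 donors if the 2.4% applied. The number of donors with only non-surgical dental care cannot be derived from the Protocol.

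The gating of H8b and H6 is a weakness of uncertain size. It costs data only if users answer No to gates that, read literally, include them. A claim that these two exposures are missing in exactly the people exposed would go beyond the document.

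Severity is minor. None of the affected items is among the predictors named in the hypotheses of Section 4 or listed in Section 4.9. They belong to the other behavioural variables to be examined, and the primary comparisons survive. The corrections are still worth making because each is specific and nearly free.

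**What to change.** Amend Appendix 7 before the interview is programmed and submitted for clearance:

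- **I8:** ask it of everyone, whatever the answer to I5.
- **F10d:** open on F10c = 9.
- **F9:** 1 goes to F9b, then F10; 10 goes to F9c, then F10; all others go to F10. Apply this to all five partner blocks.
- **H8b:** skip only if H7a and H8a are both No.
- **H6:** ask if any of H3a, H4a or H5a is Yes, keeping the present route for Don't Know and Refuse at H5a.
- **H1 = Never:** skip to H3a, not H4. Otherwise the new H6 rule misses non-drinkers who smoke dagga.
- **A7:** add code 4 (HIV and HBV case), with the label hidden on screen like the others, and route it through L1 to L9. Three further lines must follow. The K1 = No skip would send code 4 past Section L. The L7 = 96 skip would send never-pregnant women past L9. The group-only labels on L1 to L8 and on L9 must admit code 4. State that case status comes from the laboratory results and that such donors count in both 1a and 1b.

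The cost is a short set of skip and code edits, a matching change to the data dictionary, a test run of each route, and a few extra seconds for the respondents now asked. Sample size and planned analyses do not change.
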